9.4.2 Analysis of the Primary Efficacy Endpoint(s)

As this is a one-arm study and there are no comparative analyses to be made, all of the primary endpoints will be analyzed to determine the average and standard deviation within the total

patient population. In the event that inspiratory breath data could not be collected or were unreliable because of digital IS power interruptions, mouth obstructions that preclude IS use, or other events that may influence digital IS use or inspiratory breath data collection, data from that day will be excluded for the patient.

9.4.3 *Analysis of the Secondary Endpoint(s)*

No secondary endpoints are dependent on findings of primary endpoints. Average change in blood oxygen saturation and pain scores over time will be calculated across the course of each patient's postoperative stay. The change in volume of inspiratory breaths will also be calculated across the course of each patient's postoperative stay. This will also be evaluated against both the baseline IS measurement taken preoperatively as well as pulmonary function lab results. The average and standard deviation of flow rates and time spent at different flow rates will also be calculated. The time spent below or above the target 200ml/s-800ml/s range will be calculated for each inspiratory breath, and used to measure the percentage of attempted inspiratory breaths that fell within this range. As this is a one-arm study and there are no comparative analyses to be made, all of the secondary endpoints will be analyzed to determine the average and standard deviation within the total patient population.

9.4.4 *Safety Analyses*

Not applicable.

9.4.5 *Baseline Descriptive Statistics*

Not applicable.

9.4.6 *Planned Interim Analyses*

Not applicable.

9.4.7 *Sub-Group Analyses*

Not applicable

9.4.8 *Tabulation of Individual Participant Data*

Individual patient data will be stored with a randomized patient number instead of their name (e.g., 001, 002, etc).

9.4.9 *Exploratory Analyses*

Not applicable.

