3 STUDY OBJECTIVES AND ENDPOINTS

OBJECTIVES	ENDPOINTS	JUSTIFICATION FOR ENDPOINTS
Primary		
The primary objective is to evaluate the effect of a multifeatured digital IS and integrated phone app on patient adherence to incentive spirometry. Together the device and app will include the following functions: an auditory and haptic reminder cue, visual and auditory cues to guide exercise completion, exercise gamification, and data tracking and visualization features.	The primary endpoints are totality and consistency of incentive spirometry adherence. Specifically, total adherence is a measure of the number of inspiratory breath attempts performed with the digital IS per day, and the consistency of adherence is a measure of the percent of hours in which at least one inspiratory breath was attempted using the digital IS.	The number and frequency of inspiratory breath attempts with the digital IS will be evaluated to assess patient adherence to incentive spirometry.
Secondary		
The secondary objective is to evaluate metrics relating to lung function to assess post-surgery lung recovery in patients using the digital IS.	The secondary endpoints are postoperative blood oxygen saturation (SpO ₂), postoperative pain scores, preoperative pulmonary function spirometry results, and postoperative inspiratory breath quality. Pain scores will be on a scale from 0 (no pain) to 10 (unbearable pain). Specifically, quality refers to inspiratory volumes achieved over time and the flow rate at which inspiratory breaths were taken.	Blood oxygen saturation, pain scores, preoperative spirometry results, and inspiratory breath quality will be evaluated to assess post-surgery lung recovery in patients using the digital IS.
Tertiary		
The tertiary object is to evaluate patient user experience of the digital IS device.	A tertiary endpoint will be survey responses collected from patients at discharge. Please see attached survey for survey questions.	These will be used to assess user experience of the device and companion app if applicable.

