6.2 Preparation/Handling/Storage/Accountability

6.2.1 Acquisition and accountability

Prior to patient enrollment, devices and extra replacement mouthpieces will be delivered to the clinical team, who will distribute the devices to patients during each patient's pre-op holding period. Each patient will receive their own personal device to keep. If a device is deemed to be no longer functional, a replacement device will be produced and delivered. Determinants of functionality will be accuracy of inspiratory breath metrics, and proper function of adherence-promoting systems (reminders, live exercise guidance, data collection and transfer to app) and electronic components of the device (speaker, LED Screen, button, battery). These features will be tested prior to returning or delivering any devices to the clinical team.

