6.2.4 Preparation

The device must be prepared in the following fashion:

- 1) If the device battery is not charged, connect the device to a power cord connected to an external power outlet.
- 2) Turn on the device and, if the patient has downloaded the accompanying app, open the mobile app on smartphone/tablet.
- 3) Ensure strong WiFi connection is active.

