8 STUDY ASSESSMENT AND PROCEDURES

8.1 Efficacy Assessments

Study Procedures and Evaluations:

- 1) Patient identification and eligibility screening:
 - a. Once a potential participant is identified as already scheduled for a lung resection surgery, the clinical team will determine whether the patient satisfies the eligibility criteria.
 - b. Any additional eligibility criteria that cannot be identified or evaluated via Penn Charts will be reviewed and confirmed by the clinical team following receipt of signed ICF forms.
- 2) Patient visit and informed consent:
 - a. If any additional eligibility criteria need to be screened due to a lack of information in Penn Charts, the patient will be asked relevant questions after providing necessary informed consent to the clinical team.
 - i. This will take place in the doctor's office that is private. Note that in-patient hospital stay will not be billed to the study as the hospital stay is unrelated to participation in the study.
- 3) Patient spirometry testing at the pulmonary function laboratory
 - a. This is already done as part of routine care. This is not a study intervention. Lab results from spirometry testing will be a secondary endpoint.
- 4) Device intervention during patient visit
 - a. After receiving informed consent, during preoperative holding, the clinical team will give the patient one digital IS, facilitate the download of the companion app onto the patient's personal mobile device if applicable, and obtain a baseline inspiratory volume measurement.
 - b. Post-surgery, the clinical team will teach patients how to perform breathing exercises with the digital IS and instruct them regarding the quantity, frequency, and volume of inspiratory breaths to perform throughout their hospital stay.
 - i. While the digital IS is powered on, an auditory and haptic reminder will occur every 15 minutes to remind the patient to perform their breathing exercises. The patient has full autonomy as to when and how often to use the digital IS. Digital IS usage and inspiratory volume data will be collected by the device whenever it is used by the patient.
 - ii. At minimum twice per day, the clinical team will collect pain scores. This is already done as part of routine care. This is not a study intervention.

- iii. Every 4 hours, the clinical team will record a patient's SpO2. This is already done as part of routine care. This is not a study intervention.

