9.4 Statistical Analyses

9.4.1 General Approach

The data collected from the digital incentive spirometer for an individual patient, which will include timestamps of inspiratory attempts and inspiratory volume, will first be screened for false readings which are defined as an inspiratory attempt for which an inspiratory volume is ≤ 100.0 mL. False readings may occur from improper use of the device or the patient being interrupted during an inspiratory attempt, and will not be included in the analysis. To determine the total incentive spirometry adherence for a patient, the number of inspiratory breath attempts performed with the digital IS per day will be calculated and then averaged across the length of the patient's visit (or number of days the IS was in use). To determine the consistency of incentive spirometry adherence throughout postoperative stay, the number of 1 hour intervals in which at least one inspiratory breath was attempted using the digital IS will be calculated and represented as a percent of the total number of hours the digital IS was powered on and recorded metrics.

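### The day-exclusion rule in Section 9.4.2 treats non-use, which is the primary outcome, like failed recording, so adherence may be overstated by an amount the documents do not allow to be computed

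*Combined protocol and SAP*

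**What the plan says.** - **Endpoints (Section 3).** In the plan's words, "total adherence is a measure of the number of inspiratory breath attempts performed with the digital IS per day". Consistency is the percentage of hours with at least one attempt. Both measure use.
- **Exclusion rule (Section 9.4.2).** The sentence opens with a condition: "In the event that inspiratory breath data could not be collected or were unreliable because of digital IS power interruptions". It then names "mouth obstructions that preclude IS use", and ends with a catch-all and the unit removed: "or other events that may influence digital IS use or inspiratory breath data collection, data from that day will be excluded for the patient".
- **Denominators (Section 9.4.1).** Breaths per day are averaged over the length of the visit or, alternatively, "or number of days the IS was in use". Consistency is taken over hours in which the device was on and recording.
- **Who controls use (Section 8.1).** "The patient has full autonomy as to when and how often to use the digital IS".
- **Device faults are foreseen.** Section 6.2.1: "If a device is deemed to be no longer functional, a replacement device will be produced and delivered". Section 6.2.4: "If the device battery is not charged, connect the device to a power cord connected to an external power outlet".
- **Length of stay (Section 1.1).** On average 2-3 days, with participation capped at 1 week.

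The plan does not define unreliable data or a minimum length of interruption. It does not say who decides on an exclusion or when, and it plans no count of excluded days and no analysis that keeps them.

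**The concern.** Two different situations share one rule. In the first, breaths were taken but not captured because of a sensor, power or transfer fault. That is missing data. In the second, something stopped or discouraged the patient from using the device. Nothing was lost in recording, and the true count for that time is low or zero. In a study of adherence that count is the result.

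The rule's own example of a mouth obstruction belongs to the second situation, and the catch-all covers events that affect use as well as those that affect collection. The opening condition does not separate the two, because a device that cannot be used also collects nothing.

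The unit removed makes this worse. Breaths are timestamped, yet a short interruption can discard every valid hour of the day. The only planned primary result is a mean and standard deviation without a comparator, so nothing else in the analysis would show that days had been lost. This point is about days within patients who continue on the device; patients who discontinue are a separate matter.

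**Working it through.** **No plan figure to reproduce.** The sample size of 30 (Section 9.2) rests on expected recruitment, and Section 9.1 states no hypotheses. The documents give no frequency of excluded days and no level of use on them, so both are assumed below.

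**Inputs.** f = share of patient-days excluded (assumed 10% to 30%). r = true use on those days relative to other days (assumed). Excluded days are taken to be unrelated to a patient's usual level of use. Stay = 2 or 3 days (Section 1.1).

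**1. Effect of the rule.** With mean m on unaffected days, the all-days mean is m(1-f+f*r) and the rule reports m. The ratio is 1/(1-f+f*r).

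| f | r | 1-f+f*r | Rule against all-days mean |
|---|---|---|---|
| 10% | 0.5 | 0.95 | +5.3% |
| 10% | 0.3 | 0.93 | +7.5% |
| 20% | 0.3 | 0.86 | +16.3% |
| 30% | 0.3 | 0.79 | +26.6% |
| any | 1 | 1 | 0% |
| 20% | 1.25 | 1.05 | -4.8% |

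A simulation of 30 patients with 2- or 3-day stays (assumed between-patient coefficient of variation 0.5, 4,000 replicates) agreed at r=0.3: 7.5%, 16.3%, and 26.5% to 26.8%.

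For scale only, take m as 35.4 per day, the reminder arm of the cardiac surgery trial cited in Section 2.2. The all-days mean would be 35.4 x 0.95 = 33.6 in the first row and 35.4 x 0.86 = 30.4 in the third.

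**2. Pure capture failure.** Suppose use was normal (r=1) but half the day's record was lost. Dropping the day gives no bias. Counting the truncated record as a full day gives 1-0.5f, which understates by 5%, 10% and 15% at f = 10%, 20% and 30%.

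**3. Both at once.** Suppose use was halved and half of what remained was lost. The rule gives 1/(1-0.5f): +5.3%, +11.1%, +17.6%. Keeping the recorded count gives (1-0.75f)/(1-0.5f): 0.925/0.95, 0.85/0.90, 0.775/0.85, or -2.6%, -5.6%, -8.8%. The two results lie on either side of the truth, which is the reason for reporting both.

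**4. Weight of one day.** One excluded day is 1/2 = 50% of a 2-day stay or 1/3 = 33% of a 3-day stay. At f=20%, the expected number of patients losing every day is 30 x 0.2^2 = 1.2 with 2-day stays and 30 x 0.2^3 = 0.24 with 3-day stays.

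**The case against.** The strongest reply is that the rule is narrower than its catch-all suggests. An event alone removes nothing: the data must also be missing or unreliable because of it. That is correct. A reader might infer that every day with an event affecting use is dropped, and low-use days with it. The text does not support this, because a day with low use and reliable recording stays in. What remains is that non-use can itself meet the condition, as with a mouth obstruction.

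A reader might also infer that dropping device-failure days must inflate adherence. It need not: if use was normal on those days, dropping them is unbiased, and keeping a truncated count would understate (step 2). Nor do the documents say that exclusions will be chosen after usage has been seen. They are silent on who decides and when. The study is unblinded (Section 6.3) and any listed member may process data (Section 10.1.8.1), so nothing prevents it.

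Finally, the study is single-arm and exploratory, and no test or decision threshold depends on the estimate. That stands, and it limits the importance of the point without removing it.

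**Conclusion.** The point holds in limited form. Section 9.4.2 does not distinguish non-use from non-recording, it removes whole days, and its criterion is not objectively defined. Followed as written, it can overstate both breaths per day and consistency. The effect on consistency is more limited where the device was off, because Section 9.4.1 already leaves those hours out.

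The size cannot be computed from the documents. Under the assumptions shown it runs from none (r=1) through +5% (f=10%, r=0.5) and +16% (f=20%, r=0.3) to about +27% (f=30%, r=0.3). It would be negative if use on excluded days were above normal. Upward bias is a plausible risk, not a demonstrated result.

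The effect is on the estimate and its interpretation; type I error and power do not come into it. Importance: moderate.

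**What to change.** 1. **Section 9.4.2, what is missing.** Treat as missing only sensor, power or data-transfer failures documented in the device or cloud log, identified before breath counts are reviewed. State in advance whether an uncharged battery is a power failure or non-use.
2. **Section 9.4.2, what stays.** Keep days with working recording and low or zero use for patient or ward reasons, counted as observed.
3. **Unit of exclusion.** For capture failures, drop only the affected hours from consistency. For breaths per day, either scale the count to recorded powered-on time or exclude the partial day, and name the choice now. Never count a truncated day as complete.
4. **Section 9.4.1, denominator.** Use one fixed denominator, postoperative in-hospital days, less only days excluded under item 3. Without this change, zero-use days can still be lost through the days-in-use alternative, and rewording Section 9.4.2 alone would not bring them back.
5. **Reporting.** Give excluded hours and days by reason, with an all-days result (excluded days counted as recorded) beside the primary mean and standard deviation.

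**Cost.** Two reworded paragraphs, a short failure log and slightly more programming. Reported adherence may be lower.

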6.1.2 Dosing and Administration

The device will be administered to the patient in the following manner. When patients are in pre-operative holding, nursing staff will record a baseline measurement of inspiratory volume with the digital IS and facilitate patients linking their device to the mobile app if patients have a compatible smartphone. Following surgery, the attending clinical staff will teach patients how to perform breathing exercises with the digital IS and instruct them regarding the quantity, frequency, and volume of inspiratory breaths (once every ~15 minutes, with an initial target inspiratory volume of at least 500 mL) to complete during their postoperative stay. For patients that are able to download the mobile app, the mobile app will include additional instructional material on how to use the digital IS device that patients can access at any time.

After initial instruction by the attending clinical team, the patient will perform inspiratory breaths with the digital IS device independently throughout their hospital stay. To perform an inspiratory breath, the patient will empty their lungs with a large exhale, put the mouthpiece of the device to their mouth, and take a deep inspiratory breath. While the patient is using the device, they will be prompted for each exercise step by audio and visual cues, and their resulting inspiratory volume will be displayed on the device screen after each breath.

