- Timestamped inspiratory breath data (inspiratory volume over time, inspiratory air flow rate over time) – will be used in the “final data set”
- Blood oxygen saturation - will be used in the “final data set”
- Pain scores - will be used in the “final data set”
- Digital incentive spirometer device identification key – will be used in the “final data set”
- Pulmonary function lab spirometry results – will be used in the “final data set”
- Discharge survey responses – will be used in the “final data set”

Separately, our consent forms (which are stored on Presbyterian Medical Center servers and are not transferred to any other location or computer):

- Patient Name
- Date of Study Participation
- Randomized Alphanumeric Key to Label Patient Data
- Digital incentive spirometer device identification key

At the end of the study, all records will continue to be kept in a secure location for as long a period as dictated by the reviewing IRB and Institutional policies. All other data/information will not be stored beyond the scope of the patient's engagement with the study.

Patient data (timestamped inspiratory breath data, blood oxygen saturation data, pulmonary function lab spirometry results, age, weight, height, sex at birth, and pain scores) will be tagged with a randomized alphanumeric combination that will distinguish the data from one another amongst study participants. Patient names, medical record numbers, and birthdates will only be used in the initial screening process and study intervention administration, and they will not appear on data used for analysis and results. The only set of data maintained with patient names, medical record numbers, and birthdates will be internally stored on Presbyterian Medical Center servers and on consent forms.

Study participant research data will be shared via the private secure cloud-based database accessible only to study members or PennBox for study analysis. Inspiratory breath data collected with the digital IS systems will be uploaded directly to the secure cloud-based database via the HUP or PPMC WiFi. Blood oxygen saturation data, pulmonary function lab spirometry results, age, weight, height, sex at birth, and pain scores will be stored on Presbyterian Medical Center computers and will not be transferred electronically (e.g., via email) to any other computer, except to study members via PennBox. A certificate of confidentiality will not be required for this study.

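### Is the percentage of breaths within 200-800 mL/s unusable because section 9.4.3 states no cut-off?

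*Combined protocol and SAP*

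**What the plan says.** The endpoint table in section 3 makes breath quality a secondary endpoint, where "quality refers to inspiratory volumes achieved over time and the flow rate at which inspiratory breaths were taken". Section 9.4.3 gives the flow part two pieces of analysis. The first is general: "The average and standard deviation of flow rates and time spent at different flow rates will also be calculated". The second concerns the target range: "The time spent below or above the target 200ml/s-800ml/s range will be calculated for each inspiratory breath", and that time is then "used to measure the percentage of attempted inspiratory breaths that fell within this range". All secondary endpoints are summarised by mean and standard deviation across patients.

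The only screen on individual breaths is in section 9.4.1, which removes "false readings which are defined as an inspiratory attempt for which an inspiratory volume is ≤ 100.0 mL". It acts on volume, not on flow or time. Section 10.1.3 lists the recorded breath data as "inspiratory volume over time, inspiratory air flow rate over time" and keeps them in the final data set. No section gives an allowed time outside the range, a rule for breath start and end, or the flow at which the device starts recording.

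**The concern.** A percentage of breaths needs a yes/no decision for each breath, but section 9.4.3 supplies only a duration. The step from one to the other is missing.

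The omission looks serious because of how a breath is taken. Section 6.1.2 says "the patient will empty their lungs with a large exhale" before inhaling, so inspiratory flow begins at zero, rises, and falls back to zero. Every breath crosses 0-200 mL/s twice. If being within the range meant no time outside it, no fully recorded breath would qualify, however well performed. Any other result rests on a tolerance or trim that the plan does not state, so two analysts could report different percentages from the same traces. With no comparator arm, a difference in definition would not cancel out.

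**Working it through.** The plan gives no expected value for this percentage, so there is no figure to reproduce. The check asks when 0% arises, how far the result moves with the cut-off, and whether percent of time in range would be more stable.

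**Inputs.** From the plan: the range 200-800 mL/s. Assumed, because the plan gives nothing: peak flow P log-normal with median 600 mL/s and log-SD 0.35; breaths either half-sine or trapezoidal. Breath duration is scaled to 1.

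**Half-sine breath, flow = P sin(πt).**
- Share of time below 200 mL/s = (2/π) asin(200/P).
- Share above 800 mL/s, for P > 800, = 1 − (2/π) asin(800/P).
- P = 400: 33% outside. P = 600: 22%. P = 800: 16%, the minimum for this shape. P = 1000: 13% below + 41% above = 54%.

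**Trapezoid, rise and fall each a share r of the breath.**
- Share below 200 mL/s = 2r × 200/P. Share above 800 mL/s, for P > 800, = 1 − 2r × 800/P.
- With r = 0.05 and P = 600: 0.10 × 200/600 = 3.3% outside.

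**When 0% arises.** The share below 200 mL/s is positive for every P in both shapes, so zero tolerance on a full trace passes no breath. Two conditions are needed, zero tolerance and recording from below 200 mL/s, and the plan states neither. If recording ran only at or above 200 mL/s, zero tolerance would reduce to a peak of at most 800 mL/s. The chance of a peak between 200 and 800 is Φ(ln(800/600)/0.35) − Φ(ln(200/600)/0.35) = 0.794, so about 79% of breaths would pass.

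**How far the cut-off moves the result** (percent of breaths counted as within):

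| Allowed share of time outside | Half-sine | Trapezoid, r = 0.05 | Trapezoid, r = 0.10 |
|---|---|---|---|
| 0 | 0 | 0 | 0 |
| 5% | 0 | 67 | 0 |
| 10% | 0 | 79 | 67 |
| 20% | 21 | 79 | 79 |
| 25% | 46 | 79 | 79 |
| 50% | 89 | 79 | 79 |

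The 67% entries follow from P(400 ≤ peak ≤ 800) = 0.671: with r = 0.05, a 5% tolerance requires 0.10 × 200/P ≤ 0.05, which is P ≥ 400. The wide movement belongs to rounded breaths. For flat-topped ones the choice matters only at small tolerances.

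**Whether percent of time in range is more stable.** For half-sine breaths from the same peak distribution, the mean percent of recorded time in range is about 70% if recording starts from zero flow, 79% from 100 mL/s, and 92% from 200 mL/s. It needs no tolerance, but it moves by about 92 − 70 = 22 percentage points with a recording threshold the plan does not give.

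**The case for a change.** The best case for a change is that the reported value is itself the result. A cut-off chosen after the data are seen could move it widely, while fixing one in advance would take a sentence or two. Flow rate is also a named part of a secondary endpoint, and planning to measure time below 200 mL/s implies that at least some such flow is recorded, which makes the 0% reading more than hypothetical. With recording thresholds of 50, 100 or 150 mL/s, zero tolerance still gives 0%.

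Much of this stands: the percentage is not uniquely defined, and a cut-off set later would be post hoc. Three things limit its force. If any excursion were disqualifying, there would be no reason to measure its duration, so zero tolerance is not the natural reading. The large swings come from one assumed breath shape and one assumed distribution of peaks. The flow traces are kept in the final data set, so whichever cut-off is used can be stated beside the result and others shown with it.

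**Conclusion.** No change follows. This is a missing detail that an analyst would fill sensibly, since a rule returning 0% for every patient would be recognised at once as uninformative. Claiming that the plan itself yields 0% goes too far: that needs a zero-tolerance rule the plan does not state and a recording threshold it does not give.

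Little depends on the figure. Section 9.1 marks hypotheses as not applicable, section 9.2 bases the 30 patients on expected case numbers, and no success criterion uses this percentage. The primary endpoints, inspired volume, and the mean and standard deviation of flow do not depend on the cut-off. Percent of time in range is a reasonable preference, but it lies close to the planned time at different flow rates and carries its own dependence on breath boundaries, so it is not clearly better.

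The strict 0% needs only flow that passes continuously from and back to zero, with the sub-200 mL/s part recorded. The other percentages rest on the assumed shapes and peak distribution and show only how sensitive the summary could be.
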